Outcomes: Images will be evaluated qualitatively and quantitatively. Data will be submitted to Avid for qualitative analysis. Images will be visually examined by a trained radiologist or nuclear medicine physician who is blinded to the subject diagnosis and will be reported as either A β elevated (AD-like) or A β non-elevated (not AD-like). Qualitative interpretation will be performed in the following manner: the images will be reviewed using a black-white scale with maximum intensity of the scale set to the maximum intensity of all brain pixels. A elevated scan will have at least one area where the grey matter is more intense than adjacent white matter or at least 2 brain areas where the grey white contrast is reduced or absent. For quantitative evaluation, standard uptake values (SUV) will be calculated using SPM software in 6 cortical areas (frontal cortex, temporal cortex, parietal cortex, precuneus, anterior and posterior cingulate) and the cerebellum. SUV ratios (SUVR) for cortical target areas relative to the cerebellum will also be calculated and a global mean SUVR will be calculated from the average across all cortical target areas.

Statistical Analyses for Aim 1: This is a two-arm, 2:1 randomized, controlled clinical trial comparing 52 weeks of aerobic exercise to control intervention. Based on drop out rates from those who have completed our exercise trials (2 of 53 [4%] dropped out of the TEAM study and 1 of 11 [9%] dropped out of ADEPT), we conservatively estimate that 15% of the subjects will drop out of the study, leaving approximately 85 subjects for analysis. We will perform analyses based on intent-to-treat to maintain the benefits of the randomization. Per protocol analyses will also be conducted among the subjects that complete a minimum of 80% of their sessions. To further assess the response to aerobic exercise, we will conduct analyses that replace the primary explanatory factor (treatment group) with continuous measures of increase (change from baseline) in aerobic fitness (VO₂peak). This will allow us to assess the aerobic fitness hypothesis which states that aerobic fitness gains mediate neural benefits of exercise.

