We hypothesize that 52 weeks of aerobic exercise will lower amyloid burden as measured by Florbetapir PET imaging. Amyloid burden will be measured at baseline and at 52 weeks as a ratio of standard uptake values in six regions of interest to the cerebellum. Our primary amyloid burden outcome measure will be the 52-week change in Florbetapir cortical-to-cerebellar ratio averaged across these six regions of interest. The primary intent-to-treat analysis for amyloid burden will compare the change from baseline to 52 weeks between our two treatment groups using the two-sample t-test. Similar analyses will be conducted for each of the ratios for the six regions of interest individually (secondary measures), and for per-protocol analyses described above. Given the single primary measure for this aim, no multiplicity adjustment will be made and secondary endpoints will be clearly indicated as such in resulting manuscripts. To evaluate the appropriateness of our

approach (two-sample t-test), residual analysis will be conducted. This will include visual inspection of the residuals and comparison of the estimated standard deviation across groups to assess homogeneity of variances. If these diagnostics indicate concerns with our parametric approach, appropriate alternative strategies, such as nonparametric methods like the Wilcoxon rank-sum test or data transformation, will be utilized. Ordinary least squares (OLS) regression models will be used for the per protocol analyses that will assess increase in aerobic fitness as continuous measures with amyloid burden outcomes. Model assessment for these OLS models will also be conducted by assessing model assumptions through residual analyses (e.g., predicted versus residual plots, quantile-quantile [q-q] plots, etc.).

Aim 2: Determine if aerobic exercise attenuates structural brain changes in preclinical AD and those without elevated amyloid.

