We have identified primary endpoints for intent-to-treat analyses between treatment groups within each study aim: change in amyloid burden (Aim 1); hippocampal atrophy (Aim 2); and change in executive function (Aim 3). Other endpoints and analyses will be described in resulting publications as secondary. For all analyses the traditional type I error rate of $\alpha=0.05$ will be used. We will use two-sided tests to further protect against spurious results. Our primary intent-to-treat analyses will be based on the two-sample t-test. **Table 2** presents the power for each aim of our study corresponding to our primary measures. Anticipated effect sizes are presented using Cohen’s d (expected average group difference divided by the assumed, common standard deviation). We assumed 15% of our 100 enrolled subjects will be lost to attrition, so power calculations assumed 56 subjects in our exercise intervention arm and 28 subjects in our control group.

Table 2. Anticipated study power

Study aim	Primary measure*	Effect size (Cohen’s d)	Power
Aim 1	Amyloid burden	0.79	92.9%
Aim 2	Hippocampal volume	0.66	81.4%
Aim 3	Executive function	2.32	>95%

*Primary measures are change from baseline to 52-week follow-up.

Aim 1: A 78 week study assessing Bapineuzumab¹¹⁹ in AD demonstrated a mean change in cortical PIB retention (average across six cortical regions) of -0.09 (0.16 SD) for those treated with Bapineuzumab (n=20) and 0.20 (0.09) for those on placebo (n=7). Given the differences in our proposed study (preclinical AD sample, lower expected amyloid burden, shorter duration) we determined power allowing exercise to have a lower effect size. An effect size only 40% as large will produce a Cohen’s d of 0.79. Thus, Aim 1 will have 93% power to detect this conservative anticipated effect of exercise on amyloid burden (and 81.9% power to detect 30% of the Bapineuzumab effect size).

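### The form of the primary t-test is not stated; if it is the pooled test, 2:1 allocation makes it sensitive to unequal SDs, and the named fallbacks do not cure that

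*Combined protocol and SAP*

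**What the plan says.** Statistical Analyses for Aim 1 describes a "two-arm, 2:1 randomized, controlled clinical trial" and compares 52-week change "between our two treatment groups using the two-sample t-test". The sections for Aims 2 and 3 and the Sample Size Justification use the same test. None says whether the variances are pooled.

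The Aim 1 section then plans residual inspection and a "comparison of the estimated standard deviation across groups to assess homogeneity of variances". If these raise concern, "appropriate alternative strategies, such as nonparametric methods like the Wilcoxon rank-sum test or data transformation, will be utilized". No threshold or decision rule is given. Aim 2 adopts the same approach by reference. Aim 3 describes residual checks only for its additional mixed models.

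The Sample Size Justification defines Cohen's d with one SD shared by both arms, sets a two-sided 5% level, and works with 56 exercise and 28 control completers. The Aim 1 effect comes from a 78-week drug study in AD, with a mean change in PIB retention of -0.09 (SD 0.16) "for those treated with Bapineuzumab (n=20) and 0.20 (0.09) for those on placebo (n=7").

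**The concern.** Checking homogeneity of variances and assuming a common SD both point to the pooled t-test; a Welch test would need neither. The pooled standard error weights the arm variances by sample size, whereas the true standard error gives the smaller arm's variance more weight. At 1:1 the two nearly agree. At 2:1 they do not: the test is conservative when the larger arm is the more variable and liberal when the smaller arm is.

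The plan looks for this problem, but the remedies it names are aimed at non-normality. The rank-sum test also loses its 5% size when the arms have the same centre and different spread. A transformation does not in general equalise the spread of change scores that straddle zero. Either remedy would also move the analysis away from the mean change defined as the primary measure. With no trigger, the primary test is settled only after the arm SDs have been seen.

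At stake are the size and power of the primary tests, and whether the primary p-value is fixed in advance.

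**Working it through.** **Inputs.** From the Sample Size Justification: n = 56 and 28; two-sided 5%; Aim 1 reference SDs 0.16 (n=20) and 0.09 (n=7), difference 0.20 - (-0.09) = 0.29; Aim 2 reference SDs 0.74 and 0.69 (exercise), 0.80 and 0.80 (control), correlation 0.95. Assumed here: normal data, and the reference SDs as one scenario for this trial.

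**The plan's own figures.** Pooled reference SD = √[(19×0.16² + 6×0.09²)/25] = 0.1463. Then 0.29/0.1463 = 1.982, and 40% of that is 0.793. Power at 56/28 is 92.9% by normal approximation, against 92.9% in Table 2. So a common pooled SD underlies the stated power.

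**Size of the pooled test, large-sample formula.** Let k = pooled SE / true SE; size ≈ 2[1 - Φ(1.96k)].

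- Exercise 0.16, control 0.09. Pooled variance = (55×0.0256 + 27×0.0081)/82 = 0.01984. Pooled SE = √[0.01984×(1/56 + 1/28)] = 0.0326. True SE = √(0.0256/56 + 0.0081/28) = 0.0273. k = 1.193: the confidence interval is 19% too wide and size is 1.9%.
- SDs reversed. Pooled variance = (55×0.0081 + 27×0.0256)/82 = 0.01386. Pooled SE = 0.0273, true SE = 0.0325. k = 0.837 and size is 10.1%.

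**Size by simulation at 56/28** (200,000 null trials per row; the check-then-switch rule is assumed to be an F-test at 5% followed by Wilcoxon, because the plan states none):

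| SD exercise / control | Pooled t | Wilcoxon | Check, then Wilcoxon | Welch |
|---|---|---|---|---|
| Equal | 5.0% | 4.8% | 5.0% | 5.0% |
| 0.16 / 0.09 | 2.0% | 3.4% | 3.3% | 5.0% |
| 0.09 / 0.16 | 10.0% | 7.7% | 7.8% | 5.0% |
| 1.25 / 1 | 3.5% | 4.1% | 3.8% | 5.0% |
| 1 / 1.25 | 6.9% | 5.9% | 6.5% | 5.0% |

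A pooled t-test after transformation (100,000 trials, assumed common mean change 0.05) does no better. With 0.16/0.09, log(x+1) gives 2.2%, √(x+1) 2.1% and cube root 6.7%. With the SDs reversed they give 11.1%, 10.3% and 11.9%. At 68/34 (120 enrolled less 15%) the pooled sizes are about the same: 2.1% and 10.1%.

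**Power at 56/28 with SDs 0.16/0.09.** At 0.087 (30% of 0.29): pooled 79%, Welch 88%. At 0.116 (40%): pooled 96.6%, Wilcoxon 96.9%, Welch 98.7%. The plan's own 81.9% for the 30% case is not a benchmark here: with a common SD and a two-sided test it comes to about 72 to 73%, which is a separate matter.

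**Cost of Welch when SDs are equal.** Power is within 0.6 points of the pooled test, and interval width within 1%.

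**Aim 2.** Change SD = √(s₀² + s₁² - 2ρs₀s₁). Exercise: √(0.5476 + 0.4761 - 2×0.95×0.74×0.69) = 0.231. Control: √(2×0.64×0.05) = 0.253. The difference 0.09 + 0.07 = 0.16, divided by √[(0.231² + 0.253²)/2] = 0.242, gives the stated d of 0.66. With these SDs k = 0.970 and the pooled size is about 5.7%.

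**Aim 3.** Only d = 2.32 is given. Without arm SDs nothing can be computed.

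**Precision of the Aim 1 SD ratio.** F = 0.0256/0.0081 = 3.16 on 19 and 6 df, two-sided p = 0.16; the 95% interval for the SD ratio of 1.78 is 0.78 to 3.17.

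**The case against.** The strongest reply is about direction. In the Aim 1 reference the active arm is the more variable, and it is also the larger arm here, so both the pooled test and Wilcoxon err on the safe side. A reader might infer from the 10% figure that this trial's type I error is inflated. The documents do not support that: the figure needs the control arm to be the more variable by the same ratio. This stands.

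A reader might also take the reference as showing that the arms' SDs do differ. It has seven placebo patients, its interval for the ratio includes 1, and it concerns a different drug, tracer, population and duration. This stands too; the trial's own ratio and its direction are unknown.

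A third reply is that an intervention without effect adds no spread, so zero mean effect with very unequal SDs is an unlikely null. If individual effects are independent of untreated change, going from 0.09 to 0.16 needs an effect SD of √(0.16² - 0.09²) = 0.132, more than the planned mean effect of 0.116. Effects spread evenly from 0 to 0.232 on a base SD of 0.146 raise it only to √(0.146² + 0.067²) = 0.161, a ratio of 1.10. This weakens the size argument but not the power argument, which concerns a real effect.

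Last, the pooled form is an inference and the fallback list is open, so Welch is not excluded. That is correct, but a list with no trigger, consulted after the SDs are seen, leaves the primary test unfixed.

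**Conclusion.** The point holds as a gap in pre-specification. The form of the primary t-test is not stated, the text implies the pooled form, and the remedies named for unequal SDs do not restore 5% size under 2:1 allocation.

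Its size depends on SDs that are not known. With the Aim 1 reference SDs the consequence is lost power, 9 points at a difference of 0.087 and about 2 points at 0.116, with size about 2% pooled and 3% Wilcoxon. Inflation, to about 10% pooled and 8% Wilcoxon, is confined to the reversed case. The Aim 2 figures lean that way only slightly (about 5.7%). It would therefore be wrong to conclude that the p-values of all three primary endpoints are in error: Aim 2 is barely affected on its own figures, and for Aim 3 nothing can be said. Since the two references lean in opposite directions, the plan cannot rely on the error being conservative.

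The figures assume normal data and 56 and 28 completers. The check-then-Wilcoxon results also assume the F-test trigger described above.

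**What to change.** In the analysis sections for Aims 1 to 3, and in the Sample Size Justification, name the Welch (unequal-variance) two-sample t-test, two-sided at 5%, as the fixed primary test of 52-week change. Remove the provision that lets diagnostics replace the primary test. Keep the diagnostics for description, and keep Wilcoxon and transformed analyses as labelled sensitivity analyses.

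This is about one sentence, with no change to sample size or data collection. If the SDs turn out equal, the loss is under 1 point of power.

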This is a randomized controlled trial of 52 weeks of aerobic exercise on sedentary individuals with preclinical AD (n=70) and those with non-elevated cerebral amyloid (n=50) The KU ADC will screen a total of 400 cognitively normal older adults with Florbetapir PET to achieve our enrollment goal. Participants will be randomized in a 2:1 ratio to active aerobic exercise vs. control using randomization sequences generated by the study statistician ([name]). Exercise interventions will be rigorously controlled and supervised in a community-based network of KUMC approved facilities across the Kansas City area. Given our history of 5% drop out over a 6-month exercise trial, we are projecting a 15% annual dropout rate. Participants will have Florbetapir PET and MRI before and after 52 weeks of exercise. Cognitive testing will be completed at baseline, 26-, and 52 weeks. Figure 1 provides an overview of the screening and study events described in more detail below.

Fig. 1 Study Flow and Events

Timeline and Overview of Study Events

Timeline: We anticipate initiating screening of participants within 2 months of funding and beginning enrollment and the intervention within 4 months. Enrollment will be ongoing with screening of 400 participants occurring over three years (~ 3 participants a week) with enrollment completed in the middle of the 4th year of the grant. The final participants will complete the 52-week intervention in the middle of the 5th year, allowing time to complete data analyses and prepare manuscripts.

Screening: The KU ADC will screen a total of 400 participants 65 years of age and older to establish a sufficient cohort (n~120 given an estimated 30% will have evidence of cerebral amyloid) to enroll 70 preclinical AD and 50 amyloid nonelevated participants into the intervention. Screening will include a standard clinical and cognitive evaluation (KU ADC Registry or similar cognitive impairment screening) and Florbetapir PET.

Baseline Evaluation: The baseline evaluation will consist of the following outcome assessments (methodological details provided below) : brain MRI, cognitive testing, physical function assessment (aerobic fitness testing for VO₂ peak, DEXA scan for body composition, and physical function), , physical activity, and phlebotomy.

[figure not shown]
26-Week Evaluation: At 26 weeks (+/- 1 week),, participants will return for an in-person evaluation to repeat cognitive testing and assessments of physical activity.

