Statistical Analyses for Aim 2: We hypothesize that aerobic exercise will attenuate atrophy in the precuneus and hippocampus, two regions consistently identified with atrophy in preclinical AD and the earliest stages of AD. Volume measures of the hippocampus, precuneus, and of the whole brain (continuous variables) will be collected at baseline and 52 weeks. The primary measure of brain atrophy will be hippocampal volume.

The primary intent-to-treat analysis for atrophy will compare the change from baseline to 52 weeks between our two treatment groups. The two-sample t-test of the observed changes will be used for this comparison. Similar models will be generated for precuneus volume and whole brain volume, and for the per-protocol analyses described above. Given a single primary measure for this aim, no multiplicity adjustment will be made and secondary endpoints will be clearly indicated as such in resulting manuscripts. Model assessment and alternative approaches will follow as described in Aim 1.

Aim 3: Determine the effects of aerobic exercise on cognition in individuals with preclinical AD and those without elevated amyloid.

Rationale: Substantial evidence, including our own (see background above), exists demonstrating that aerobic exercise has a preferential effect on cognition, particularly in executive functioning.^{69, 70, 135} Thus, our primary outcome measure is executive function. This study, however, extends previous exercise-cognition studies as it seeks to provide evidence of a specific effect on AD pathophysiology (i.e., disease modifying effect) of aerobic exercise on AD-related pathophysiological change in preclinical AD. Thus, we will also assess key cognitive domains that are associated with asymptomatic cerebral amyloid deposition.

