CSF and imaging studies indicate that declines in global cognitive ability¹³⁶ and episodic memory (verbal-based,⁵⁰ visuospatial-based,^{137, 138} or both¹³⁹⁻¹⁴¹) are associated with the presence of cerebral amyloid. Thus, secondary outcomes include verbal and visuospatial-based episodic memory measures where we expect decline on these measures will be associated with higher amyloid deposition. Visuospatial ability is an excellent marker of preclinical AD (leading diagnosis by at least 3-years)¹⁴²⁻¹⁴⁵ and was the strongest cognitive indicator for PIB-positive status in a longitudinal study on healthy aging. Visuospatial ability is also strong indicator of executive functioning ability.¹⁴⁶ Although studies of the cognitive effects of aerobic exercise have not resulted in major improvements in episodic memory, no studies have assessed the cognitive effects of exercise in a cohort of individuals with preclinical AD who have expected accelerated rates of decline in episodic memory. By selecting amyloid elevated individuals, we are targeting individuals with preclinical AD who may benefit most from potential disease-modifying effects of aerobic exercise on AD pathophysiology. Thus secondary outcomes include verbal and visuospatial-based episodic memory measures, where we expect decline on these measures will be associated with higher amyloid deposition.

Additionally, three reports indicate cognitive decline in preclinical AD may be mediated by structural changes in the hippocampus^{136, 139, 140} and the concept of preclinical AD posits that hippocampal atrophy is a downstream effect of amyloid deposition. Moreover, this mediation hypothesis may explain a recent finding from Kraemer and colleagues¹⁴⁷ where better visual memory performance was associated with less hippocampal atrophy in exercising nondemented older adults.¹³⁹ Thus, we will test the mediation effect of hippocampal atrophy on the relationship between exercise and cognitive decline over 52-weeks across all 3 outcomes. We anticipate visual memory to be the strongest of the multiple indicators.

Data Acquisition: All participants complete a 2- 3 hour neuropsychological test battery at baseline, 26-weeks, and 52-weeks. This battery includes selected tests with demonstrated responsiveness to aerobic exercise and sensitivity to change in preclinical AD. These tests will be aggregated into several domains: Executive Function, Visual Memory, and Verbal Memory, General Health, Emotional Health.

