Outcomes: Cognitive domains of Executive Function, Verbal Memory, and Visual Memory are face valid aggregates of related subtests that have generated moderate to large effect sizes across several reviews on cognition and aerobic exercise when aggregated. We have expertise using Confirmatory Factor Analysis (**CFA**) to determine the best fitting empirical model of data and create factor score weights that are sensitive indicators of cognitive change.^{157, 158} CFA is a common method used to aggregate true score (common) variance across multiple subtests and attenuate error. Thus, factor scores yield more reliable estimates of cognitive ability than individual tests because they are purer indices of ability.^{159, 160} This is desirable because cognitive performance in aging individuals is highly variable. Individual subtests are not as efficient as CFA-

based composite scores. We have shown in previous work^{142, 161} that longitudinal declines in cognitive ability can best be characterized with a model¹⁶² of specific mental abilities.

Statistical Analyses for Aim 3: This intent-to-treat analysis will use a two-sample t-test to compare change from baseline to 52 weeks between our treatment and control groups on the primary (executive function) and secondary outcomes (verbal and visual memory). Secondary endpoints will be clearly indicated as such in resulting manuscripts; therefore no further multiplicity adjustments will be made. Because cognition is measured at three time points (baseline, 26-, and 52-weeks), linear mixed models will also provide additional information such as to the functional form of the potential benefits of exercise (e.g., linear increasing benefit over time, initial benefit within 26 weeks that is sustained, etc.). Assessments of these linear mixed models will be conducted by evaluating model assumptions through residual analyses (similar to that described above).

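### Aim 3's primary t-test omits participants without a 52-week score and ignores their 26-week cognition, although the planned mixed model could use it

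*Combined protocol and SAP*

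**What the plan says.** Aim 3, Data Acquisition, schedules the "neuropsychological test battery at baseline, 26-weeks, and 52-weeks". Statistical Analyses for Aim 3 then sets the primary test: "This intent-to-treat analysis will use a two-sample t-test to compare change from baseline to 52 weeks between our treatment and control groups". The same paragraph adds that "linear mixed models will also provide additional information such as to the functional form of the potential benefits of exercise". It gives no week-52 contrast, visit coding or covariance structure for that model.

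Sample Size Justification fixes the ranking for every aim: "Our primary intent-to-treat analyses will be based on the two-sample t-test", and "Other endpoints and analyses will be described in resulting publications as secondary".

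On attrition, Study Procedures says: "Given our history of 5% drop out over a 6-month exercise trial, we are projecting a 15% annual dropout rate". Statistical Analyses for Aim 1 expects that "15% of the subjects will drop out of the study, leaving approximately 85 subjects for analysis". The power calculation uses 56 exercise and 28 control participants. No imputation rule, missing-data assumption or sensitivity analysis for dropout appears anywhere.

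Aim 2 uses the same kind of test ("The two-sample t-test of the observed changes will be used for this comparison"), as does Aim 1, but PET and MRI are taken only at the start and at 52 weeks.

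**The concern.** A change score needs a 52-week value. With no imputation rule, the primary test can include only participants who have one. They are analysed as randomised, so this is not the per-protocol set, but it is not everyone randomised either. That dropouts are left out is an inference, since no sentence says so. It is a firm one, because the plan's own analysis counts already exclude them.

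Aim 3 differs from Aims 1 and 2 because it has a mid-study measurement. A participant who leaves after week 26 has a post-randomisation cognitive score that the primary test discards.

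At stake is the comparison of the randomised groups. If dropout is related to cognitive course, and occurs at different rates or by different mechanisms in the two arms, those still present at week 52 are no longer comparable. One arm is asked for a year of exercise sessions, the other receives education plus scheduled calls and visits, so identical dropout cannot be presumed. The documents report no dropout by arm, and the bias could favour either arm.

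**Working it through.** **1. The plan's own figure.** With d = 2.32 and 56 against 28, the standardised difference is 2.32 / √(1/56 + 1/28) = 2.32 / 0.2315 = 10.0. Power exceeds 99.9%, consistent with the stated >95%. The same method gives 92.7% for Aim 1 (stated 92.9%) and 81.4% for Aim 2 (stated 81.4%). The power table therefore counts only participants with a 52-week value. Attrition is allowed for in number but not in its possible effect on bias.

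**2. How many are affected.** At the current target of 120, 15% × 120 = 18 lack a 52-week score. If the 5% six-month history holds for the first half of the year, 5% × 120 = 6 leave by week 26 and 12 after it. If 15% is instead spread at a constant rate, 120 × (1 − √0.85) ≈ 9 leave in each half.

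**3. Size of the bias.** The documents give no within-person correlation, dropout by arm or dropout mechanism, so these are assumptions:
- 80:40 randomised, and changes standardised to SD 1;
- correlation r = 0.6 between 26- and 52-week change;
- log-odds of dropout rising by 1 for each SD of worse 26-week change;
- all dropouts seen at week 26.

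Let Z be standardised 26-week change and d(Z) = 1/(1 + exp(−(a − Z))), with a set so that the average dropout is p. Completers' mean 26-week change is shifted by s(p) = E[Z(1 − d(Z))]/(1 − p). The t-test's bias is r × [s(exercise) − s(control)].

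Numerical integration gives s = 0.047 at 5%, 0.074 at 8%, 0.082 at 9%, 0.108 at 12%, 0.133 at 15%, 0.157 at 18%, 0.173 at 20% and 0.193 at 22.5%. For 20%/5% the bias is 0.6 × (0.173 − 0.047) = 0.076.

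Simulation (20,000 trials per scenario) compared the t-test with the likelihood estimate from an unstructured model of 26- and 52-week change:

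| Dropout, exercise/control | Formula, t-test | Simulated t-test | Simulated model |
|---|---|---|---|
| 20% / 5% | +0.076 | +0.075 | 0.000 |
| 22.5% / 0% | +0.116 | +0.115 | −0.001 |
| 5% / 20% | −0.076 | −0.074 | +0.002 |
| 18% / 9% | +0.045 | +0.047 | +0.002 |
| 12% / 8% | +0.020 | +0.022 | +0.002 |
| 15% / 15%, same mechanism | 0.000 | −0.002 | −0.002 |
| 15% / 15%, outcome-related in exercise only | +0.080 | +0.082 | +0.002 |
| 15% / 15%, outcome-related in control only | −0.080 | −0.079 | 0.000 |

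At 20%/5%, correlations of 0.4 and 0.8 give a t-test bias of +0.051 and +0.100.

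**4. Against the standard error.** At 20%/5%, 64 and 38 participants remain, and √(1/64 + 1/38) = 0.205. The simulated values for the two methods are 0.200 and 0.201. The bias is 0.075/0.20 ≈ 0.4 of one standard error at 20%/5%, and 0.115/0.20 ≈ 0.6 at 22.5%/0%. Null rejection (t-test / model) is 6.7% / 4.7% at 20%/5%, 9.0% / 5.0% at 22.5%/0%, and 6.6% / 4.8% at 15%/15% with outcome-related dropout in exercise only.

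**5. If some dropouts also miss week 26 (20%/5%).** Bias of t-test / model is +0.076 / +0.021 when one third miss it, +0.077 / +0.033 when half do, and +0.076 / +0.076 when all do.

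**The case against.** The strongest reply is that the model's near-zero bias is built in. Every scenario above makes dropout depend only on the observed 26-week change, which is the missing-at-random condition the model needs. That is right. If dropout at 20%/5% instead depends on 52-week change itself, two separate simulations give about +0.13 for the t-test and +0.08 to +0.09 for the model. With half the dropouts unseen at week 26, they give +0.12 to +0.13 against +0.10 to +0.11. The gain shrinks to roughly 0.02 to 0.04 SD but does not reverse.

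Second, the 6/12 split sets an observed rate against a projection the plan itself calls conservative, which pushes dropout into the second half of the year. Under a constant rate about half of dropouts leave before week 26, and the +0.077 / +0.033 row is the relevant one. This stands as a limit on the benefit.

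Third, the bias is small unless the arms differ clearly: +0.02 at 12%/8%, and nil with equal dropout and a common mechanism. The 9.0% rejection rate needs no control dropout at all. There is also almost no precision to gain. This stands too.

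Fourth, the t-test is clearly pre-specified, power allows for attrition, the mixed model is already planned, and the trial is a pilot. All true, but high power does not correct bias. If the two analyses disagree, the stated ranking makes the t-test decide.

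**Conclusion.** The concern holds. As written, the primary Aim 3 test can use only participants with a 52-week score, and it discards the 26-week cognition of those who leave later. The planned analysis that can use those data ranks below it and lacks the specification needed to serve as the main test.

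The consequence is conditional and moderate. Where dropout is outcome-related and the arms differ clearly in its rate or mechanism, the t-test's bias is about 0.05 to 0.12 SD in either direction. It is near zero where the arms behave alike. These sizes rest on the assumed correlation, dropout slope and rates by arm. The stated power is not overturned. For Aims 1 and 2 no mid-study outcome is being discarded, so the point there is only to describe the analysed set accurately.

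**What to change.** In Statistical Analyses for Aim 3 and in Sample Size Justification:

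- Make the linear mixed model primary for executive function. Include all randomised participants with any cognitive score, using baseline, 26 and 52 weeks, with visit as categorical and an unstructured covariance. Name the difference between arms in change from baseline to week 52 as the test.
- State that the model assumes scores are missing at random given those observed. Add a sensitivity analysis that shifts the missing 52-week scores by arm, because the model does not remove bias when dropout depends on unseen scores.
- Keep the t-test as a supportive analysis of participants with a 52-week score.
- Report dropout by arm and by timing, before or after week 26.

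For Aims 1 and 2, state that the t-tests include participants with 52-week imaging, analysed as randomised. Imputation there is optional and of unproven benefit.

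The cost is wording only: no new visits or data are needed, and precision is not lost in the scenarios examined. The remaining limits are the missing-at-random assumption and the lack of any recovery from participants who leave before week 26.
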